Chronic HBV (CHB) is an emerging health crisis in the US. Approximately 15%-40% of those with chronic HBV will develop serious liver diseases during their lifetime including decompensated cirrhosis and hepatocellular carcinoma (HCC).^{4, 9-11} Asian Americans (AA) have the highest liver cancer mortality rates and the highest prevalence of CHB.¹² Further, inadequate disease monitoring and care will contribute to poorer outcomes and increased healthcare costs. Indeed, the soaring medical costs associated with HBV infection are estimated to be as high as \$1.5 billion each year.^{1, 13-15}

Early monitoring and adherence to recommended HBV disease management guidelines improves health outcomes, prevents expensive complications such as cancer treatments or liver transplants, and reduces premature deaths.^{1, 11, 15, 16-20}

Despite the health and economic advantages of early monitoring and regular follow up care for HBV, few people are receiving such care. One study indicated that fewer than 50,000 US HBV patients have sought early treatment for HBV, meaning that less than 10% of those eligible for treatment actually receive monitoring and regular follow up care.²⁰ Asian Americans with CHB may not seek care because they “feel well”^{21, 22}, have lower access to care (e.g., no regular healthcare provider, need for English translator), face more economic (e.g., lack of health insurance, low income) and cultural barriers (e.g., negative perceptions of Western medicine, stigma of HBV disease), or have a low level of knowledge about HBV and the benefits of care.^{21, 23-29} Even among Asian American CHB patients receiving care, adherence to monitoring and treatment guidelines is low as 40%-53% at 12 month follow-up.^{21, 30}

2. Significance of the Proposed Study:

CHB is a major contributor to the racial/ethnic health gap and HBV disparities in mortality between AAs and Whites are widening.^{6, 12} Early monitoring and adherence to recommended CHB management guidelines are an essential part of a comprehensive approach to improving CHB control for reducing incidence and mortality rates of liver cancer.^{1, 7, 21-23, 31, 32-35} Patient adherence to regular follow up tests every 6 and 12 months is associated with optimal CHB control.¹¹ Unfortunately, early onset of liver problems comes without apparent symptoms and only consistent follow-up testing allows for early treatment. However, adherence rates to monitoring guidelines are poor among AA CHB patients.

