This application provides a unique opportunity to address these gaps in the literature and respond to this critical health disparity issue by investigating a Patient Navigator-led Text Messaging Intervention (PMNI).

II. OBJECTIVES

The described study is a collaborative effort between the lead agency, Center for Asian Health of Temple University and its long-term clinical partners in greater Philadelphia area and New York city.

III. STUDY DESCRIPTION

1. Overview of Study Design

Patient-centered and community-based participatory research approach will be applied to the randomized comparative trial design, a range of quantitative and qualitative evaluation methods, and implementation of a HBV intervention to improve care for underserved AA chronic HepB patients. Temple U. Center for Asian Heath (CAH) partnered with Federally Qualified Community Health Center (FQHC) and community primary care clinics that serve low-income Chinese, Korean and Vietnamese patients to conduct a comparative trial to evaluate the effectiveness of the patient navigator-led plus mobile phone text messaging intervention (PNMI), an interactive patient-centered culturally and linguistically appropriate approach. The study builds on a strong foundation of 20-year clinic-community-academic partnership. As shown in our pilot studies, CBPR approach were applied to engage patient partners and stakeholders in project planning, recruitment, delivery, evaluation and dissemination.

The proposed study is a 2-arm randomized comparative trial with individual patients as the unit of randomization. Bilingual patient navigators will be recruited and trained to deliver the PNMI intervention to help patients improve adherence to HBV monitoring tests on time.

2. Selection of Patient Participants

Inclusion Criteria: Patients (N=500) will be included in the study if they meet the following criteria:

- self-identified Chinese, Korean and Vietnamese ethnicity (these three Asian subgroups consist of the largest number of immigrants from countries with high prevalence of HBV infection,
- age 18 and above
- not enrolled in any chronic HBV adherence management intervention (to prevent a potential program impact),
- medically diagnosed chronic HBV infection with positive for hepatitis B surface antigen (HBsAg) for more than six months, and
- not had HBV monitoring tests for more than six months.

Exclusion Criteria: Patients will be excluded from the study for the following conditions:

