- diagnosed with cirrhosis, hepatocellular carcinoma, liver failure and liver cancer (The purpose of regular follow up tests is to detect early signs of CHB

complications). Monitoring the progression of CHB complications is different in schedules and tests),

3. Intervention Procedures

- 1) Study Timeline
- **The duration of the project**
1/1/2015-12/31/2017
- **The duration of a subject's participation in the study.**
12-13 months
- **The duration anticipated to enroll all subjects.**
12 months
- **The estimated date that the investigators will complete the study.**
December 31, 2017

2) Intervention delivery

Following randomization, intervention patients will receive PNMI in-person education sessions from patient navigators who navigate patients through the program. PNMI focuses on recognizing patients as active participants in their own health care. PNMI intervention bilingual patient navigator-led HBV management; text messaging; clinical support assistance and HBV management education visual aids.

4. Statistical considerations

Data Analysis Plan

The primary outcome analysis will calculate the difference in adherence rates between two groups (PNMI – SC) at 6m or 12m post-intervention. Bonferroni multiple comparison adjustment will be used for two primary hypothesis tests. The difference of two binomial proportions and its 97.5% (due to Bonferroni adjustment) 2-sided confidence interval (C.I) will be calculated for inference. We expect the tests for intervention effects for both 6m and 12m post intervention will be highly significant with effect size substantially larger than 20%, based on our pilot study data and other screening studies. Though not a primary hypothesis, we will examine if the adherence rate has declined at 12m from that at 6m by calculating a 95% C.I for the difference of two rates. If the decline is statistically significant, a booster intervention after 6m post intervention may be needed for future disseminations. To control for known and postulated factors, a number of variables will be included as covariates in most analyses, including (1) race, (2) clinics, (3) education, (4) age, (5) gender, (6) time living in U.S., (7) birthplace, and (8) English proficiency

5. Withdrawal of Subjects

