The purpose of this study is to improve HBV routine/regular monitoring adherence. Subjects in intervention group of this study will receive education on knowledge about HBV monitoring and navigation assistance for their further medical care needs. Participants in comparison group will also receive standard care for their routine HBV care. Stay with adherence of HBV monitoring is a critical practice to ensure early detection of HBV progression and capture the right momentum of early treatment for HBV.

9. Informed Consent

The consent process will be taken place on site of collaborating clinical partners and CBOs located in greater Philadelphia area and New York City. Project staff will inform participants of the nature and purpose of the study as well as participant rights. A consent and HIPPA form will be provided to participants prior to participation in the study. Participants will be informed about the purpose and nature of the study, intervention and comparison contents of the project, foreseeable risks, benefits of participation and right of participants, confidentiality statement, voluntary participation statement, and institutional IRB contact and research contact. Participants will be encouraged to contact the PI or IRB regarding any concerns about component of the study. Participants are also informed that they may choose withdrawing at any time during the study without penalty.

10. Data Safety and Monitoring

To ensure all regulatory requirements of PCORI are met, a Data Safety Monitoring Committee consists of five individuals who are expert in the study areas and who are familiar with the community but having no conflict of interest with the proposed project.

The Monitoring Committee will meet in person or teleconference two times a year over the course of the study, or at an intermediate time, if needed, in response to immediate needs/concerns on IRB related issues, implementation of protocol, and any unanticipated problems.

11. Adverse Event Reporting

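### The valid raw primary comparison leaves the plan's eight listed covariates unused; a prespecified covariate-adjusted risk difference would be an inexpensive, optional precision gain

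*Combined protocol and SAP*

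**What the plan says.** Section III.4 (Data Analysis Plan) defines the primary contrast as PNMI minus standard care in adherence rate at 6 and 12 months, with Bonferroni adjustment for two tests. The inference rule is explicit: "The difference of two binomial proportions and its 97.5% (due to Bonferroni adjustment) 2-sided confidence interval (C.I) will be calculated for inference". The plan expects both tests to be "highly significant with effect size substantially larger than 20" percent, read here as percentage points.

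After a sentence on the non-primary comparison of 12 with 6 months, the section states that "a number of variables will be included as covariates in most analyses, including (1) race, (2) clinics, (3) education, (4) age"; the list continues "5) gender, (6) time living in U.S., (7) birthplace, and (8) English proficiency". The stated reason is control of known and postulated factors. Precision is not mentioned, and neither a model nor an adjusted effect measure is named.

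Section III.1 has "individual patients as the unit of randomization". Section III.2 gives N=500. The documents do not state an allocation ratio, a control rate used for design, or an allowance for loss to follow-up. The nearest figure to a control rate is in the background, where "adherence to monitoring and treatment guidelines is low as 40%-53% at 12 month follow-up".

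**The concern.** In an individually randomised trial with a binary outcome, adjusting for prognostic baseline covariates can shorten the confidence interval for the same risk difference without recruiting anyone. This plan intends to adjust most of its analyses for eight variables, yet its primary inference, as written, uses none of them. Some are plausibly prognostic on the plan's own account: the background gives the need for an English translator and cultural and economic barriers as reasons why patients do not seek care.

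What is at stake is interval width at the expected effect, and some power if the true effect is well below 20 points. Validity is not at stake.

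**Working it through.** **Reproducing the plan's own figure.** Two tests at an assumed family-wise 0.05 give 0.05/2 = 0.025 each, hence intervals of 1 - 0.025 = 97.5%. This agrees with the plan. The two-sided critical value is z = 2.2414.

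**Inputs.**
- From the documents: N=500, two arms, individual randomisation, 97.5% intervals, expected effect above 20 points.
- Assumed: 1:1 allocation (250 per arm); control adherence p0 = 46.5%, the midpoint of the background's 40% to 53%; outcomes observed on all 500; covariate R2 between 0 and 20%; 8 clinics and 15 covariate terms (7 clinic, 2 subgroup, 6 others).

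**Raw analysis.** SE = sqrt[(p0(1-p0) + p1(1-p1))/250]. At a 20-point effect, p1 = 0.665:
- SE = sqrt[(0.248775 + 0.222775)/250] = 0.0434
- half-width = 2.2414 x 0.0434 = 9.73 points
- power = Φ(0.20/0.0434 - 2.2414) = 0.991

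The same formula gives 0.877 at 15 points and 0.503 at 10 points.

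**Adjusted analysis.** Adjusted SE = r x raw SE. The ratio r comes from simulating a logistic model with standardisation: 500 patients, 8 clinics holding 4% to 22% of patients each, 4,000 runs per setting. As a plausibility check, the large-sample factor sqrt(1-R2) times the simulated cost of fitting 15 useless terms (about 1.015) gives 0.975 x 1.015 = 0.99, 0.949 x 1.015 = 0.963 and 0.894 x 1.015 = 0.908. These agree with the simulated 0.99, 0.965 and 0.91. Equivalent patients are 500/r² - 500.

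| Covariates | r | Half-width at 20 points | Power, 20 points | Power, 15 points | Power, 10 points | Equivalent patients |
|---|---|---|---|---|---|---|
| Raw analysis | 1 | 9.73 | 0.991 | 0.877 | 0.503 | 0 |
| Adjusted, R2 0 | 1.015 | 9.88 | 0.989 | 0.867 | 0.490 | -15 |
| Adjusted, R2 5% | 0.99 | 9.64 | 0.992 | 0.884 | 0.512 | +10 |
| Adjusted, R2 10% | 0.965 | 9.39 | 0.994 | 0.901 | 0.535 | +37 |
| Adjusted, R2 20% | 0.91 | 8.86 | 0.998 | 0.933 | 0.591 | +104 |

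**Sensitivity.**
- *Control rate.* At 40% or 53%, raw power moves by at most about 0.015.
- *Allocation.* At 2:1, power at 15 points is 0.830 raw and 0.84 to 0.90 adjusted (R2 5% to 20%).
- *Loss to follow-up.* An assumed 20% loss leaves 200 per arm. Raw power is then about 0.97 at 20 points and 0.79 at 15.
- *Number of terms.* At R2 5% the simulated ratio with 15 terms ranged from 0.984 to 1.002. With 25 terms (1,500 runs per setting, 15-point effect) it was about 1.02 at R2 0, 1.01 at 5% and 0.96 at 10%. Richer coding therefore removes the gain at the low end.
- *Clinic and subgroup overlap.* Section III.1 refers to "community primary care clinics that serve low-income Chinese, Korean and Vietnamese patients", so the two may coincide in part. If 95% of each clinic's patients came from one subgroup, precision was almost unchanged, but the logistic fit failed in 0.1% to 2.7% of runs. Pooling clinics with fewer than 30 patients cut failures to at most 0.14% with no loss of precision.
- *Validity.* Null rejection averaged 0.0279 raw and 0.0282 adjusted, against a nominal 0.025.

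**The case against.** The strongest reply is that nothing needs repair. The plan names an effect measure, an interval level and the purpose of inference. The covariate sentence comes later, after a non-primary comparison, and says most analyses, not all. A raw difference is unbiased under individual randomisation, and at the effect the plan expects it has ample power. All of this stands.

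The gain also rests on an R2 for which the documents give no figure. The list holds demographic, language and clinic variables. Entry already requires more than six months without monitoring tests, which largely fixes one obvious predictor of later testing. This does not show that R2 is low, but nothing supports the 20% end, and the 104-patient figure comes only from there. That stands too.

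A reader might infer that the primary analysis is undefined, or that the word most leaves room to pick the better of two results. The documents do not support either. The natural reading is an unadjusted primary, and nothing suggests selection. Nor do the documents show that race is ambiguous, since entry is limited to three self-identified ethnicities. They do not show that some patients lack a clinic either: Section III.9 says "The consent process will be taken place on site of collaborating clinical partners and CBOs located in greater Philadelphia area and New York City", which concerns only where consent is taken.

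What survives is narrower. The plan means to collect and use these covariates anyway, and using them in the primary analysis would cost little and could help.

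**Conclusion.** This is an optional precision improvement of low severity, and the plan is not in error on this point. At a 20-point effect the 97.5% half-width would go from 9.73 points to between 9.64 and 8.86 for R2 of 5% to 20%, or widen to about 9.9 if the covariates are not prognostic. The trial's conclusion would rarely change. The power gain is larger only if the true effect is 10 to 15 points: at 15 points, from 0.877 to between 0.884 and 0.933.

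These figures assume 1:1 allocation, 46.5% control adherence, complete follow-up and about 15 model terms, none of which the documents state as design inputs. The powers are best-case, because loss to follow-up lowers them for both analyses. At R2 of about 5% the gain is close to nil, and it disappears with generous coding. The stronger claim that the primary analysis is invalid or short of power is not supported.

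**What to change.** Before outcome data are examined, state that the primary analysis at each of 6 and 12 months is a covariate-adjusted risk difference from a logistic model with standardisation, with a 97.5% interval. This keeps the estimand, the scale and the Bonferroni level. Specify:

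- a closed covariate set drawn from the eight listed, with few terms each, and race coded as the Chinese, Korean or Vietnamese subgroup if that is what is meant;
- a rule for pooling small clinics, for example those with fewer than 30 patients, and for dropping subgroup terms that clinic makes non-estimable;
- a rule for missing covariate values, for example single imputation from baseline data without using arm or outcome;
- the raw difference as a labelled sensitivity analysis, and as fallback if the model does not converge.

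The cost is a short addition to the Data Analysis Plan, slightly more analysis work, and a standard error about 1.5% to 2% larger if the covariates prove uninformative. No further patients or variables are needed. If the sponsor prefers the raw primary, one sentence saying that it governs and that adjusted results are supportive is a sound alternative, which forgoes the possible gain.
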